4.1.3 Adverse Events

The accepted regulatory definition for an AE is provided in [Section 6.1.1](#). All medical occurrences from the time of first dose that meet this definition must be recorded. Important additional requirements for reporting SAEs are explained in [Section 6.2](#).

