5.4 MISSING DATA HANDLING

General Considerations: Subjects lost to follow-up (or who dropped out) will be included in statistical analyses up to the point of their last evaluation.

Duration of Response and Progression-free Survival: Data for subjects without disease progression or death will be censored at the date of the last tumor assessment and before the initiation of alternative anticancer therapy. The censoring rules details will be provided in the Statistical Analysis Plan (SAP).

Overall Survival: Data for subjects who have not died will be censored at the date of the last date known to be alive.

Safety: Missing or partial start and end dates for AEs and concomitant medications will be imputed according to prespecified, conservative imputation rules. No other imputation of values for missing data will be performed.

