3 STUDY OVERVIEW

3.1 Study Design

This clinical trial is a phase 2, multicenter (approximately 70 global centers), open-label study in subjects with histologically documented MCL, who have relapsed after or were refractory to ≥1 (but not >5) prior treatment regimens. Subjects will be enrolled and will take 100 mg of acalabrutinib twice per day (bid) in repeated 28-day cycles.

Treatment with acalabrutinib may be continued until disease progression or an unacceptable drug-related toxicity, whichever occurs first. Dose modification provisions are provided in the study protocol. All subjects who discontinue study drug will have a safety follow-up visit 30 (+7) days after the last dose of acalabrutinib. An early

Acerta Pharma Confidential Page 6 of 28

termination visit is required for any subjects who permanently discontinued study drug for any reason including disease progression (exceptions included death, lost to followup, or withdrawal of consent).

All subjects will have hematology, chemistry, and urinalysis safety panels done at screening. Once dosing commences (Day 1), all subjects will be evaluated for safety, including serum chemistry and hematology, once weekly for the first 4 weeks, every 2 weeks in Cycle 2, every 4 weeks in Cycles 3 to 12, and every 12 weeks thereafter. PK/PD testing will be done in Cycles 1 and 2. Tumor assessments will be completed at 8- to 12-week intervals during the trial.

The primary efficacy analyses will be based on investigator assessment. An Independent Review Committee (IRC) will assess the efficacy endpoints in accordance with the IRC charter provided separately from this document.

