9 MISSING VALUES

9.1 Safety Data

Imputation of partial dates will be made for AE onset and stop dates, start and end dates of concomitant medication, start date of subsequent anticancer therapy, date of initial diagnosis and death date. If dates are completely missing, no imputation will be made. For any partial date with missing year, no imputation will be made.

The general rule for imputation is:

- If only day is missing, then the 15th of the month will be used.
- If only year is present, then June 30th will be used.

If such imputation date for initial diagnosis is on or after date of first dose, the date of first dose -1 will be used. If such imputed date for subsequent anticancer therapies is before the date of last dose, the date of last dose +1 will be used.

If the imputed date is for an AE start date and is in the same year and month as the first dose date but before the first dose date, then the first dose date will be used, or if the imputed AE start date is after the AE end date, then the AE end date will be used. If the imputed date is for an AE start date and is in the same year and month as but after the last dose date + 30 days, then the last dose date + 30 days will be used.

If the imputed date is for an AE end date and is after the death date, the date of death will be used, or if the imputed AE end date is before the AE start date, the AE start date will be used.

Acerta Pharma Confidential Page 11 of 28

Statistical Analysis Plan

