10.7.1 Adverse Events

The Medical Dictionary for Regulatory Activities (MedDRA Version 19.1) will be used to code all AEs to a system organ class and a preferred term. The severity of the AE will be assessed by National Cancer Institute (NCI) Common Terminology Criteria for Adverse Events (CTCAE) Version 4.03. Study drug-related AEs are those assessed by investigator as related.

Treatment-emergent AEs are defined as those events that occur or worsen on or after the first dose of study drug, through the treatment phase, and within 30 days following the last dose of study drug.

Treatment-emergent AEs will be summarized by system organ class and preferred terms in descending order of frequency, by CTCAE toxicity grade. Drug-related treatment-emergent AEs, serious treatment-emergent AEs and drug-related serious treatment-emergent AEs, treatment-emergent AEs leading to treatment discontinuation, dose delay and dose modification will be summarized by preferred teams in descending order of frequency and by CTCAE toxicity grade.

Death information is reported in the study exit CRF for all deaths. Incidences of deaths are to be reported, along with the primary cause of death.

Acerta Pharma Confidential Page 18 of 28

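### SAP 9.1 sets a year-only adverse event start to 30 June, and its first-dose guard cannot act on that value, so an on-treatment event can be dated before first dose (minor)

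*SAP*

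**What the plan says.** SAP 9.1 imputes partial AE dates in two steps. First comes a default: the 15th when only the day is missing and, for a date with no month, "If only year is present, then June 30th will be used". Then come guards on the imputed AE start:

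- It moves to first dose if it is "in the same year and month as the first dose date but before the first dose date".
- It moves to the AE end date if it falls after that date. This clause is joined to the first by an 'or', with no order given.
- It moves to last dose + 30 days if it is "in the same year and month as but after the last dose date + 30 days".

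Other guards in the same section have no month condition. An imputed start of subsequent anticancer therapy, for example, is moved whenever it "is before the date of last dose, the date of last dose +1 will be used".

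SAP 10.7.1 counts an AE as treatment-emergent if it occurs or worsens from first dose onward, "through the treatment phase, and within 30 days following the last dose of study drug". Protocol 4.1.3 starts recording at first dose: "All medical occurrences from the time of first dose that meet this definition must be recorded". Under Protocol 6.2.1 only serious events are reported between consent and first dose. Protocol 5.4 says missing or partial AE dates are "imputed according to prespecified, conservative imputation rules".

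**The concern.** The guards test the imputed date, including a month that the rule itself supplied. When the month is unknown, June is an artefact of the default, yet the guard requires it to equal the month of first dose.

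A non-serious AE in this database should have begun on or after first dose, because recording starts there. If the rule dates it before first dose, it fails the onset test for treatment emergence and drops out of the tables that report AE frequency, a secondary endpoint. That is the opposite of a conservative rule, which would keep an event of uncertain date in the treatment period.

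**Working it through.** **Inputs.** The default dates and guards are from SAP 9.1, the treatment-emergent definition from SAP 10.7.1, the start of AE recording from Protocol 4.1.3 and 6.2.1, and the visit schedule from SAP 3.1 and Protocol Appendix 4. Counts below are calendar dates in a 365-day year, not AE rates.

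**1. First-dose guard, year-only start.** The imputed start is 30 June. The guard acts only if first dose is in June of that year and later than 30 June. No such date exists, so it acts for 0 of 365 first-dose dates. A correction is needed whenever first dose is after 30 June: 31 + 31 + 30 + 31 + 30 + 31 = 184 dates, or 184/365 = 50.4%. All 184 stay uncorrected. For example, with first dose on 1 October 2015 and AE start recorded as 2015, the imputed start is 30 June 2015, which is 31 + 31 + 30 + 1 = 93 days before first dose.

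**2. Other clauses.** The end-date clause only moves a start earlier, and so does the last dose + 30 days clause. Neither can bring 30 June forward to a later first dose.

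**3. Last dose + 30 days guard, year-only start.** A correction is needed when the window closes before 30 June: 31 + 28 + 31 + 30 + 31 + 29 = 180 dates. The guard acts only when the window closes in June, on the 1st to the 29th: 29 dates. It misses 180 − 29 = 151 (1 January to 31 May; 152 in a leap year). An AE end date inside the window repairs the record, because the end-date clause then pulls the start back.

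**4. Order of clauses.** Two cases with a partial end date in the month of first dose:

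| First dose | AE start | AE end | First-dose guard, then end-date clause | End-date clause, then first-dose guard |
|---|---|---|---|---|
| 20 January 2015 | 2015 | January 2015 | 30 June, guard idle; then 15 January (pre-dose) | 15 January; then 20 January |
| 20 March 2015 | March 2015 | March 2015 | 15 March to 20 March; then back to 15 March (pre-dose) | 15 March unchanged; then 20 March |

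So the unstated order matters for day-missing starts as well as year-only ones.

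**5. Size.** The first-dose failure needs an onset in the calendar year of a first dose given on or after 1 July, hence within 184 days (184/28 = 6.6 cycles). Safety visits in that time are "once weekly for the first 4 weeks, every 2 weeks in Cycle 2, every 4 weeks in Cycles 3 to 12". From first dose they fall on days 1, 8, 15, 22, 28, 43, 56, 84, 112, 140 and 168: 11 visits, at most 28 days apart. An onset whose month is unknown should be rare. Each subject-level event lost moves a frequency by 1/117 = 0.85 percentage points on the planned size, or 1/124 = 0.81 on the 124 subjects named in Protocol 1.5.2.

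**6. Detection figures.** The plan's probabilities of seeing at least one event, 1 − (1 − p)^117, give 69.1%, 90.6% and 99.8% for p = 1%, 2% and 5%, as stated. They do not depend on date imputation.

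**The case against.** The strongest reply is that this may affect no one. It needs an AE with no known onset month, in the year of a first dose given in July or later, with no recorded worsening, in a trial with frequent visits. The documents show no such AE, and calendar counts say nothing about how many exist. That stands and is why the point is minor. First doses in the second half of 2015 are nonetheless likely, since SAP 7 reports that enrolment could continue after the September 2015 interim analysis.

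Second, SAP 10.7.1 does not say that imputed dates decide treatment emergence, whereas SAP 10.5.2 expressly applies Section 9.1 to medications. The loss from the tables is therefore an inference. It is a reasonable one, because a guard that pulls AE starts to first dose has little other purpose.

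Third, the SAP was written to Protocol Amendment 6, and the protocol available here is a later version. The promise of conservative rules and the start of AE recording are quoted from that later text. The fault inside SAP 9.1 does not depend on either.

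A reader might infer that the first-dose guard can never correct any year-only start. That is too strong: in the January case above, if the end-date clause runs first, the start is no longer 30 June and the guard does act. A reader might also infer that day-missing starts are always handled correctly. That holds without an end date, but the March case shows it can fail under one order of the clauses.

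**Conclusion.** The concern holds as a minor error in a stated rule. Applied literally, SAP 9.1 leaves a year-only AE start at 30 June for every first dose from 1 July to 31 December of that year (184 dates). It also leaves such a start beyond the window when last dose + 30 days falls between 1 January and 31 May (151 dates), unless the AE end date pulls it back. In a further set of records with partial end dates, the result depends on an order that the SAP does not give.

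This rests on two assumptions: that treatment emergence is derived from the imputed start, and that no worsening on or after first dose is recorded. The documents do not support the inference that the reported AE frequencies are materially too low. The number of year-only starts is not given and is probably very small. Sample size, power and detection probabilities are unaffected.

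**What to change.** In SAP 9.1, replace the same-year-and-month condition in both AE-start guards with a comparison of only the reported parts of the start date: the year alone when the month is missing, year and month when only the day is missing. Then state the order:

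1. End-date clause.
2. Last dose + 30 days guard.
3. First-dose guard last: an imputed start before first dose, whose reported parts match first dose, becomes the first dose date. The exceptions are a serious event reported before dosing and an AE whose reported end date lies wholly before first dose.

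The existing rule for AE end dates follows once the start is settled. Under this wording a year-only start in the year of first dose is left before first dose for 0 of 365 first-dose dates, apart from those exceptions. Both cases in the table resolve to first dose.

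One drafting point: the end-date clause should act only when the imputed start is later than the latest date that the reported parts of the AE end date allow. Otherwise a year-only end, itself set to 30 June, can drag a start with a known later month back before first dose.

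The cost is one edited SAP rule and its program, with no new data and no protocol amendment. If tables have already been run, re-run the affected treatment-emergent tables and document the change in the clinical study report, as SAP 1 provides.

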9.2 Efficacy Data

The method for handling missing data is described in the definition for each of the efficacy endpoints. Every effort will be made to obtain complete dates for deaths. In the event of a partial or missing death date, the algorithm in Appendix13.2 will be used.

10 STATISTICAL METHODS OF ANALYSIS

10.1 General Principles

Descriptive statistics will be used to summarize disposition, demographics, baseline characteristics, baseline disease characteristics, study drug administration, efficacy and safety outcomes. Descriptive summaries of discrete data will present the sample size and the incidence as frequency and percentage. Descriptive summaries of continuous data will present the sample size, group mean, standard deviation, median, and range. Confidence intervals (CIs) may be included as appropriate.

10.2 Subject Accountability

The number of subjects enrolled by site will be presented. Subject disposition will be summarized for all enrolled subjects including the following information:

- Subject status on study drug
- Count and reason for study drug discontinuation
- Subject status on study
- Count and reason for study termination
- Time on study

10.3 Important Protocol Deviations

Important Protocol Deviations (IPDs) categories are defined and managed by the study team during the IPD reviews throughout the study before database lock. These definitions of IPD categories, sub-category codes, and descriptions will be used during the course of the study. The final IPD list is used to produce the Summary of IPDs table and the List of Subjects with IPDs.

10.4 Baseline Data

Summaries of demographics, baseline characteristics, and baseline disease characteristics will be presented for subjects in the All-treated Population.

10.4.1 Demographics

- Sex (Male, Female)
- Age (continuous)
- Age category (<65 versus ≥ 65, <75 versus ≥75)
- Ethnicity
- Race
- Region

10.4.2 Baseline Characteristics

- Height (cm)
- Weight (kg)
- ECOG performance status

10.4.3 Baseline Disease Characteristics

- Time (months) from initial diagnosis to first dose
- Tumor bulk (grouped as <5 cm, ≥5 and <10 cm, ≥10 cm)
- Tumor burden (cm²)
- Ann Arbor staging for lymphoma
- Extranodal disease
- Bone marrow aspiration and biopsy result
- Simplified MIPI score (low risk, intermediate risk, high risk)
- Refractory disease (yes/no)
- Number of lines of prior therapies for MCL (continuous and grouped as 1, 2, ≥3)
- Lactate dehydrogenase (LDH) > upper limit normal (yes/no)

10.5 Treatment and Medications

10.5.1 Prior Anticancer Therapies

A prior anticancer therapy is defined as a systemic therapy subjects received, either as a single or combination therapy, for the treatment of active MCL with a start and end date occurring before the date of first dose of acalabrutinib. Therapies given as a consolidation or maintenance of a response or remission will not be considered as a separate regimen. Preparatory regimen and transplant will not be considered as separate regimens. Prior number of regimens for MCL is the total number of lines of therapy that a subject received for MCL before he/she entered this study. The number of lines and type of prior therapy for MCL will be summarized.

10.5.2 Prior and Concomitant Medications Received for Indications Other than MCL

Data reported on concomitant medications CRF page will be used. Medications started or ended prior to first dose will be considered as prior treatment. Concomitant therapy is defined as all medications used on or after the first dose, through the treatment phase, and for 30 days following the last dose of study drug. Using this definition, a medication can be classified as both prior and concomitant. The start date and end date will be imputed based on the rules provided in Section 9.1 of the SAP. Medications with completely missing start and stop dates will be considered as both prior and concomitant medications.

Prior and concomitant medications other than antineoplastic agents or other systemic therapies for MCL after enrollment will be summarized by the World Health Organization (WHO) Drug Dictionary therapeutic class, pharmacological class, and preferred term.

10.5.3 Subsequent Anticancer Therapy for MCL

Subsequent anticancer treatments for MCL are reported on the alternative cancer therapy CRF. Treatment started after discontinuation of acalabrutinib (i.e. started after the last dose of acalabrutinib) will be considered as subsequent anticancer treatment for MCL. The start date of first subsequent anticancer treatment will be considered as the start of subsequent anticancer therapy. Subject listing of subsequent anticancer therapy for MCL will be provided.

Acerta Pharma Confidential Page 14 of 28

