3.8 WITHDRAWAL OF SUBJECTS FROM STUDY TREATMENT

The investigator, in consultation with the medical monitor, may withdraw any subject from study treatment, if, in the investigator's opinion, it is not in the subject's best interest to continue.

Any subject has the right to withdraw from the study at any time. In addition, subjects may be withdrawn from study treatment for the following reasons:

- Study treatment should be discontinued in the event of a toxicity lasting > 28 days, unless reviewed and approved by the medical monitor.
- Any subject who starts new chemotherapy or chemoimmunotherapy for the treatment of MCL should be withdrawn from study treatment.

- Any subject who has **confirmed** objective evidence of cancer progression while receiving acalabrutinib should be withdrawn from the study treatment. If there is uncertainty regarding whether there is cancer progression, the subject may continue study treatment and remain under close observation (eg, evaluated at 4-week intervals) pending objective confirmation of progression. In particular, transient worsening of disease early in therapy or during temporary interruption of study therapy (eg, for drug-related toxicity, surgery, or intercurrent illness) may not indicate cancer progression. In such circumstances, and if medically appropriate, subjects may resume therapy, and relevant clinical, laboratory, and/or radiographic assessment can be attempted to document whether tumor control can be maintained or whether cancer progression has occurred.
- Any subject whose medical condition substantially changes after entering the study should be carefully evaluated by the investigator in consultation with the medical monitor. Such subjects should be withdrawn from study treatment if continuing would place them at risk.
- Any subject who becomes pregnant should be removed from study treatment.
- Any subject who becomes significantly noncompliant with study drug administration, study procedures, or study requirements should be withdrawn from study treatment in circumstances that increase risk or substantially compromise the interpretation of study results.

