13.3 Censoring Rules for Duration of Response

Situation	Outcome	Date	Event Description/ Censoring Reason
Progression documented between scheduled visits on or before receiving subsequent anticancer therapy or data cutoff, whichever occurred first	Event	Earliest date of disease assessment documenting progression	PD
Death without documented PD and not receiving subsequent anticancer therapy on or before data cutoff	Event	Date of Death	Death
Documented PD or death after subsequent anticancer therapy and the subsequent anticancer started before data cutoff date	Censored	Date of last adequate disease assessment prior to subsequent anticancer treatment	Subsequent anticancer therapy
No documented PD or death at the time of data cutoff and subsequent anticancer therapy started before the data cutoff	Censored	Date of last adequate disease assessment prior to subsequent anticancer treatment	Subsequent anticancer therapy
Documented PD or death after subsequent anticancer therapy and the subsequent anticancer started after data cutoff date	Censored	Date of last adequate disease assessment on or before data cutoff	Data cutoff
No documented PD or death at the time of data cutoff and subject not received subsequent anticancer therapy or subsequent anticancer therapy started after the data cutoff	Censored	Date of last adequate disease assessment on or before data cutoff	Data cutoff
Withdrew consent without documented PD or death	Censored	Date of last adequate disease assessment	Withdrew consent
Lost to follow-up without documented PD or death	Censored	Date of last adequate disease assessment	Lost to follow-up

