13.4 Censoring Rules for Progression-free Survival

13.4.1 Primary Analysis of PFS

Situation	Outcome	Date	Event Description/ Censoring Reason
Progression documented between scheduled visits on or before receiving subsequent anticancer therapy or data cutoff, whichever occurred first	Event	Earliest date of disease assessment documenting progression	PD
Death without documented PD and not receiving subsequent anticancer therapy on or before data cutoff	Event	Date of Death	Death
Documented PD or death after subsequent anticancer therapy and the subsequent anticancer started before data cutoff date	Censored	Date of last adequate disease assessment prior to subsequent anticancer treatment	Subsequent anticancer therapy
No documented PD or death at the time of data cutoff and subsequent anticancer therapy started before the data cutoff	Censored	Date of last adequate disease assessment prior to subsequent anticancer treatment	Subsequent anticancer therapy
Documented PD or death after subsequent anticancer therapy and the subsequent anticancer started after data cutoff date	Censored	Date of last adequate disease assessment on or before data cutoff	Data cutoff
No documented PD or death at the time of data cutoff and subject not received subsequent anticancer therapy or subsequent anticancer therapy started after the data cutoff	Censored	Date of last adequate disease assessment on or before data cutoff	Data cutoff
Withdrew consent without documented PD or death	Censored	Date of last adequate disease assessment	Withdrew consent
Lost to follow-up without documented PD or death	Censored	Date of last adequate disease assessment	Lost to follow-up
No post-baseline adequate disease assessments	Censored	Date of first dose	No postbaseline adequate disease assessments
No baseline disease assessments	Censored	Date of first dose	No baseline disease assessment

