13.4.2 Sensitivity Analysis of PFS

A sensitivity analysis will be performed where all PD or death (including those after the start of subsequent anticancer therapy) will be considered as events. The censoring rules for this analysis are summarized below.

Situation	Outcome	Date	Event Description/ Censoring Reason
Progression documented between scheduled visits on or before data cutoff	Event	Earliest date of disease assessment documenting progression	PD
Death before first PD assessment or between adequate assessment visits on or before data cutoff	Event	Date of Death	Death
Withdrew consent without documented PD or death	Censored	Date of last adequate disease assessment	Withdrew consent
Lost to follow-up without documented PD or death	Censored	Date of last adequate disease assessment	Lost to follow-up
No documented PD or death at the time of data cutoff	Censored	Date of last adequate disease assessment on or before data cutoff	Data cutoff
No postbaseline adequate disease assessments	Censored	Date of first dose	No postbaseline adequate disease assessments
No baseline disease assessments	Censored	Date of first dose	No baseline disease assessment

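### MCL therapy with a complete start date on or before the last acalabrutinib dose falls outside the SAP's DOR and PFS censoring rules, and best response has no cut at new therapy

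*SAP*

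**What the plan says.** SAP 10.5.3 gives the definition: "Treatment started after discontinuation of acalabrutinib (i.e. started after the last dose of acalabrutinib) will be considered as subsequent anticancer treatment for MCL". It then sets the date: "The start date of first subsequent anticancer treatment will be considered as the start of subsequent anticancer therapy".

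The censoring tables rely on that term. In SAP 13.3 the DOR row reads "Documented PD or death after subsequent anticancer therapy and the subsequent anticancer started before data cutoff date", and SAP 13.4.1 has the same row for primary PFS. The censoring date is "Date of last adequate disease assessment prior to subsequent anticancer treatment". Neither table has a row for MCL therapy given while acalabrutinib continues. In the PFS sensitivity analysis of SAP 13.4.2, "all PD or death (including those after the start of subsequent anticancer therapy) will be considered as events", so new therapy plays no part there.

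Protocol 5.4 says that DOR and PFS data for subjects without progression or death "will be censored at the date of the last tumor assessment and before the initiation of alternative anticancer therapy". It does not mention the last acalabrutinib dose, and it leaves the details to the SAP. Protocol 3.6.4 prohibits other treatment for MCL during the study. Protocol 3.8 states: "Any subject who starts new chemotherapy or chemoimmunotherapy for the treatment of MCL should be withdrawn from study treatment".

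Three other SAP rules bear on the point:
- SAP 9.1 imputes partial start dates of subsequent therapy and moves an imputed date that falls before the last dose to the day after the last dose.
- SAP 10.6.1.2 classifies each subject by the best response reached at any time on study.
- SAP 10.5.2 limits the medication summary: "Prior and concomitant medications other than antineoplastic agents or other systemic therapies for MCL after enrollment will be summarized".

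**The concern.** The event that should stop follow-up for DOR and PFS is the start of another treatment for the lymphoma. The SAP ties that event to the last acalabrutinib dose, and the protocol does not. The order in Protocol 3.8 is that new therapy starts and study treatment is then withdrawn, so a start before the last dose is foreseeable. Even a same-day switch fails the SAP definition.

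Where this happens before documented progression, later assessments are credited to acalabrutinib alone, although another treatment has been given. A subject who starts the same therapy one day after the last dose is censored. In a single-arm trial no comparator absorbs the difference.

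ORR has a related but separate weakness. No rule stops a response first documented after new MCL therapy from counting, whichever side of the last dose that therapy began. The IRC endpoints are defined in the same way (SAP 10.6.2.1.4) and inherit both gaps.

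**Working it through.** **The plan's own figures.** The plan gives no figure on this point. Its power statement reproduces: Φ{[(0.40 − 0.20)√117 − 1.96√(0.20×0.80)] / √(0.40×0.60)} = Φ(2.82) = 99.8%, against a stated value above 99%. Nothing in that calculation depends on the definition.

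**Step 1: the rules side by side.** Let L be the last acalabrutinib dose and T the start of new MCL therapy, with no progression documented before T and T before data cutoff.

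| Start of new therapy | Subsequent under SAP 10.5.3? | DOR and primary PFS |
|---|---|---|
| Complete date, T after L | Yes | Censored at the last adequate assessment before T |
| Complete date, T on or before L | No | Not censored for T; later PD or death is an event |
| Partial date, imputed before L | Yes, once moved to L+1 | Censored at the last adequate assessment before the moved date |

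If a second agent starts after L, SAP 10.5.3 takes that later date as the trigger and the overlapping agent is still ignored.

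**Step 2: dependence on date completeness.** Suppose the last dose is on 20 May and new therapy starts on 10 May. With the full date recorded, the therapy is not subsequent and nothing is censored. With the day missing, SAP 9.1 imputes 15 May. That is before 20 May, so the date moves to 21 May and the therapy counts as subsequent. This assumes that the rule is applied to every start date on the alternative-therapy form.

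**Step 3: ORR.** Each subject whose first response follows new MCL therapy adds 100/n points. The denominators are 124 (subjects of this study in Protocol 1.5.2) and 117 (SAP 3.2). The documents give no count, so 1, 3 and 6 subjects are assumptions.

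| Subjects | n=124 | n=117 |
|---|---|---|
| 1 | 0.81 | 0.85 |
| 3 | 2.4 | 2.6 |
| 6 | 4.8 | 5.1 |

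These are upper bounds, because a subject who had already reached PR or CR before the new therapy adds nothing. The preliminary ORR in Protocol 1.5.2 is 80.6% of 124, or 100 responders. Removing 6 leaves 94/124 = 75.8%, still far above the 20% null.

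**Step 4: PFS.** An illustrative simulation used these assumptions:
- 117 subjects and 3,000 replicates, with exponential PFS of median 13.9 months (the ibrutinib study in Protocol 1.3).
- Accrual over 12 months (assumed), then 14 months of follow-up.
- In k subjects, therapy added 1 month before progression, delaying it by an exponential time with mean 13.9/ln 2 = 20.1 months.
- The alternative rule censors at the start of therapy, not at the preceding scan.

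| k | Mean KM median, SAP rule | Censored at start | 12-month PFS, both rules |
|---|---|---|---|
| 1 | 14.14 | 14.17 | 0.553 |
| 3 | 14.42 | 14.41 | 0.559 |
| 6 | 14.75 | 14.72 | 0.566 |
| 12 | 15.55 | 15.52 | 0.583 |

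The agreement is partly built in. The assumed delay has the same hazard as the whole cohort, which is also what Kaplan-Meier assumes for a censored subject. If the added therapy gained nothing, the SAP rule would keep the true event and censoring would remove it, raising the curve. If the gain were long, the SAP rule would give the higher curve. The direction therefore depends on a quantity the documents do not contain.

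**The case against.** The strongest reply is that such therapy is prohibited, so the gap concerns deviations and brief overlaps at a switch. The last withdrawal reason in Protocol 3.8 also covers serious noncompliance that would undermine interpretation of the results. Protocol 5.4 hands the censoring details to the SAP. The SAP was written for Amendment 6, whereas the protocol compared here is the Amendment 10 text. Censoring at new therapy is itself informative.

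Most of this limits the size of the point. It does not remove it: an analysis plan still has to say how deviations are handled, and delegating details does not explain why the last dose should decide whether a treatment counts. The amendment difference affects how the mismatch arose. The gap within the SAP stands regardless.

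A reader might infer four stronger claims that the documents do not support:
- *On-treatment MCL therapy can never lead to censoring.* SAP 9.1 makes an exception for some partial dates.
- *Section 10.5.3 inflates ORR.* The definition does not feed ORR. That exposure comes from the open response window in SAP 10.6.1.2, and changing the definition alone would leave it in place.
- *The bias in PFS and DOR favours acalabrutinib.* Later progression or death still counts as an event, and Step 4 shows no consistent direction.
- *Such therapy would appear in no output.* It is outside the medication summary of SAP 10.5.2 and the subsequent-therapy listing. The important-deviation table and listing in SAP 10.3 may capture it, although the categories are not itemised.

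**Conclusion.** The definition in SAP 10.5.3 is wrong as written. It is narrower than the rule in Protocol 5.4, it leaves overlapping MCL therapy with a complete start date without a censoring rule, and it lets the completeness of a date decide how a subject is handled. The response window is a second, separate gap.

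For ORR the effect is at most 0.81 points per affected subject at n=124, or 0.85 at n=117, and only where no response preceded the new therapy. For PFS and DOR neither the size nor the direction can be established. The one simulated scenario showed almost no difference, and its assumptions favour that result. The number of subjects is unknown and probably small. No sample-size or power figure is affected, and a change in the overall conclusion on response is not plausible at the counts considered. The point is worth correcting because the rule is inconsistent and cheap to repair. It does not show that the results are materially biased.

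**What to change.** In SAP 10.5.3, define the trigger as the first start, on or after the first acalabrutinib dose, of any anticancer therapy given for MCL, regardless of the last-dose date. Then:
- use that date in SAP 13.3 and 13.4.1;
- bring the shift to the day after the last dose in SAP 9.1 into line, so that partial and complete dates follow one rule;
- in SAP 10.6.1.2, exclude assessments after that date from best overall response, for both investigator and IRC;
- list the affected subjects with therapy, start date and last-dose date.

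The cost is SAP wording, one derived date, a few more censored times and possibly a slightly lower ORR. The extra censoring may be informative. The sensitivity analysis in SAP 13.4.2, which counts all progressions and deaths, stays as the check for PFS. Before adopting the change, confirm that the CRFs capture MCL therapy given during acalabrutinib treatment, including radiotherapy; the documents do not show this.
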